3.1.3 Reconstitution of Antiviral Immunity

Patient serum and peripheral blood mononuclear cells will be monitored for virus-specific activity by functional studies including ELISpot with appropriate viral specific peptide mixtures and available HLA-restricted epitope peptides, intracellular cytokine staining, serum cytokine profiling and/or other assays as they become available for immune profiling purposes.

3.1.4 Persistence of infused VSTs

Persistence of infused T cells will be monitored using deep sequencing and additional tests as indicated to track the TCR v-beta repertoire in the patient peripheral blood prior to and post-infusion.

3.1.5 Effects on Clinical Signs of Viral Infection

If a patient has organ involvement clinical response will be monitored. For patients with EBV lymphoma and measurable disease, response will be assessed by RECIST criteria.

3.1.6 Survival

Overall survival at 3, 6 and 12 months post VST infusion will be computed.

3.1.7 Chronic GVHD

Chronic GVHD will be assessed 3, 6 and 12 months post VST infusion.

3.1.8 Viral Reactivations

All CMV, EBV, adenovirus, BK virus, JC virus and HHV6 infections/reactivations occurring within 12 months of VST infusion will be collected. Information about infection or reactivation with other viruses may be collected as well.

CHARMS Protocol v1.0 (10.30.13)	Version 5.0 (10.6.15)
Version 2.0 (12.09.13)	Version 6.0 (08.29.16)
Version 2.1 (03.07.14)	Version 7.0 (04.26.17)
Version 3.0 (06.17.14)	Version 8.0 (05.24.17)
Version 4.0 (11.06.14)	Version 9.0 (08.10.17)

3.1.9 Secondary graft failure

Secondary graft failure is defined as initial neutrophil engraftment followed by subsequent decline in the ANC to $<500/\text{mm}^3$ for three consecutive measurements on different days, unresponsive to growth factor therapy that persists for at least 14 days in the absence of a known cause such as relapse. Secondary graft failure will be assessed at 30 days post VST infusion.

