- Safety including acute GVHD grades III-IV within 42 days of the last dose of VSTs or grades 3-5 non-hematological adverse events within 28 days of the last VST dose and that are not due to the pre-existing infection or the original malignancy or pre-existing co-morbidities as defined by the NCI Common Terminology Criteria for Adverse Events (CTCAE), Version 4.X.

Secondary Endpoints

- Antiviral responses 42 days after the first dose of VSTs
- Effects of partially HLA-matched VSTs on viral loads
- Persistence of partially HLA-matched VSTs and effects on clinical signs/symptoms
- Reconstitution of antiviral immunity at 1, 2, 3, 4,6 weeks and 3 months
- Viral reactivations within 12 months
- Secondary graft failure at 30 days
- Chronic GVHD at 3 months, 6 months and 12 months
- Clinical response to VST infusions at 6 weeks and 3 months
- Effects of HLA matching
- Effects of choosing a line with confirmed antiviral activity through one or more shared alleles
- Overall survival at 3 months, 6 months and 12 months

CHARMS Protocol v1.0 (10.30.13)	Version 5.0 (10.6.15)
Version 2.0 (12.09.13)	Version 6.0 (08.29.16)
Version 2.1 (03.07.14)	Version 7.0 (04.26.17)
Version 3.0 (06.17.14)	Version 8.0 (05.24.17)
Version 4.0 (11.06.14)	Version 9.0 (08.10.17)

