4.2.2 Assessments

All assessments are considered standard-of-care unless identified below by “*.”

Pre-Infusion

1. History and physical exam including height and weight
2. Viral loads for EBV, adenovirus, CMV, HHV6, JC virus and BK virus
3. Complete acute GVHD staging and grading information including assessments of rash, diarrhea, nausea/vomiting, weight and liver function tests
4. CBC with differential, platelet count
5. Basic chemistry
6. Liver function tests (bilirubin, alkaline phosphatase, AST, ALT)
7. Tacrolimus/cyclosporine level if on these agents
8. Pregnancy test* if female patient of childbearing potential and has received a reduced intensity transplant regimen
9. Samples for research laboratory studies*

Post-Infusion

1. Viral load for the treated virus or viruses will be collected weekly at 1, 2, 3, 4 and 6 weeks, and 3 months post-infusion. Thereafter, viral load results will be followed until 12 months post infusion as clinically indicated. Additional time points may be analyzed as clinically indicated. If the treatment team is also measuring viral loads for other viruses we will follow these results.
2. Complete acute GVHD staging and grading information including assessments of rash, diarrhea, nausea/vomiting, weight and liver function tests weekly until Day 42

CHARMS Protocol v1.0 (10.30.13)	Version 5.0 (10.6.15)
Version 2.0 (12.09.13)	Version 6.0 (08.29.16)
Version 2.1 (03.07.14)	Version 7.0 (04.26.17)
Version 3.0 (06.17.14)	Version 8.0 (05.24.17)
Version 4.0 (11.06.14)	Version 9.0 (08.10.17)

3. Chronic GVHD evaluation (if present) at 3, 6, and 12 months
4. Liver function tests (bilirubin, alkaline phosphatase, AST, ALT) at 1, 2, 3, 4, 5 and 6 and 3 months.
5. Infusion-related toxicities within 24 hours and toxicity evaluation weekly until Day 30, and acute GVHD until Day 42.
6. Steroid dose weekly until Day 42, and at 3 and 6 months
7. Samples for laboratory studies at 1, 2, 3, 4, and, 6 weeks and 3 months: 30-40mls or 6-8 teaspoons will be collected at each time point. For recipients who weigh less than 10kg the amount will be reduced to 3mls/kg. Depending on clinical and laboratory viral responses samples may be collected at additional time points.*

Research laboratory studies will include:

Assessment of virus-specific immunity as measured by serum profiling, ELIspot, intracellular cytokine staining, multimer assays and/or other assays as they become available.

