After the initial follow up for safety is complete at 30 days for toxicity and 42 days for GVHD, patients will continue to be followed per routine clinical care post transplant. We will perform laboratory follow-up studies for 3 months post-infusion or longer depending on clinical and laboratory viral responses and will assess these patients clinically at 3, 6 and 12 months to evaluate for any long term effects attributable to the VST infusion.

Table 4.2.2 REQUIRED ASSESSMENTS

	Baseline (Day 0)	7	14	21	28	35	42	90	180	365
History and physical exam	X									
CMV, EBV, adenovirus, HHV6 and/or BK virus load (if previously positive)	X	X	X	X	X		X	X		
Acute GVHD evaluation	X	X	X	X	X	X	X			
Chronic GVHD evaluation								X	X	X
Liver function tests (alkaline phosphatase, bilirubin, AST, ALT)	X	X	X	X	X	X	X	X		
Tacrolimus/cyclosporine levels*	X									
Pregnancy test ¹	X									
Infusion related toxicity evaluation	X ²	X	X	X	X ³					
Steroid dose	X	X	X	X	X	X	X	X	X	
Blood and serum for ancillary laboratory studies	X ⁴	X ⁴	X ⁴	X ⁴	X ⁴		X ⁴	X ⁴		
Infections	X	X	X	X	X		X	X		
CBC with Differential	X									
Basic Chemistry	X									

* If on these agents

¹ Pregnancy test if of child bearing potential and has received a reduced intensity transplant

² This evaluation should be done within 24 hours of infusion

³ This evaluation should be done on day 30.

⁴ Research procedures beyond that required for usual care - 30-40mls or 6-8 teaspoons will be collected at each time point. For recipients who weigh less than 10kg the amount will be reduced to 3mls/kg. Depending on clinical and laboratory responses samples may be collected at additional time points before or after 90 days.

CHARMS Protocol v1.0 (10.30.13)	Version 5.0 (10.6.15)
Version 2.0 (12.09.13)	Version 6.0 (08.29.16)
Version 2.1 (03.07.14)	Version 7.0 (04.26.17)
Version 3.0 (06.17.14)	Version 8.0 (05.24.17)
Version 4.0 (11.06.14)	Version 9.0 (08.10.17)

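### Secondary graft failure needs three low neutrophil counts over at least 14 days, but it is read at day 30 and the only required blood count is at baseline

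*Combined protocol and SAP*

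**What the plan says.** The secondary endpoint list in the synopsis includes "Secondary graft failure at 30 days". Section 3.1.9 gives the definition. After initial engraftment, the ANC must fall below 500/mm³ "for three consecutive measurements on different days, unresponsive to growth factor therapy that persists for at least 14 days", with no known cause such as relapse. The same section fixes the reading time: "Secondary graft failure will be assessed at 30 days post VST infusion".

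The blood count that this needs appears in two places, both at baseline:
- In section 4.2.2, "CBC with differential, platelet count" is item 4 of the pre-infusion list. None of the seven post-infusion items mentions a blood count or ANC.
- In Table 4.2.2, the row "CBC with Differential" has a single mark, at day 0.

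Scheduled visits fall on days 7, 14, 21, 28, 35, 42, 90, 180 and 365. There is no day-30 visit as such. Footnote 3 of Table 4.2.2 ("This evaluation should be done on day 30") moves the day-28 toxicity evaluation and does not mention counts.

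Section 4.2.1 restarts the schedule at each dose, so that follow-up relates to the last dose, and section 2.4.2.5 allows repeat doses from day 28. Section 3.1.9 does not say which infusion starts the 30 days. Section 5.4 plans descriptive summaries only.

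**The concern.** The definition asks for serial dated counts over at least two weeks, while the schedule requires none after infusion and the reading date falls before a late decline can qualify. Whether a patient is classified as a failure then depends on how often the treating team happened to draw counts and on how an abstractor treats a decline still open at day 30. Two abstractors could class the same day-20 onset differently.

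At stake is the one listed endpoint aimed directly at graft function after a third-party T-cell product. The adverse-event part of the primary safety endpoint and of the dose-limiting toxicity definition (sections 3.1 and 5.3) is limited to non-hematologic events, so it does not stand in for this endpoint. Attribution also needs dated counts, because the background sections list neutropenia as a side effect of the CMV drugs (1.2) and link HHV6 to marrow suppression (1.6).

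**Working it through.** The plan states no figure for this endpoint, so there is none to reproduce. The check is a day count.

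**Inputs.** Three low values on different days, at least 14 days' persistence and reading at day 30 come from section 3.1.9. Required blood counts come from section 4.2.2 and Table 4.2.2, and visit days from Tables 4.2.1 and 4.2.2.

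**Step 1: required data.** Required post-infusion ANC values up to day 30: 0. Needed: at least 3. The pre- and post-infusion lists agree with the table, so the single baseline mark is not an artefact of how the table was read.

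**Step 2: latest onset that can qualify by day 30.** Onset + 14 ≤ 30 gives onset ≤ 16. Onsets on days 17 to 30 (14 of 30 possible days) cannot qualify at the stated reading time. If the onset day itself counts as day one of the 14, the limit is day 17 (days 17 to 30 are 14 calendar days) and 13 days are excluded.

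**Step 3: what different count schedules could confirm.** Apart from the first row, the schedules are assumptions. A case is confirmed if at least three values on or after onset span at least 14 days.

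| Count schedule | Read at | Onset days confirmable |
|---|---|---|
| As required now (none after day 0) | day 30 | none |
| Days 7, 14, 21, 28 | day 30 | 1–14 (last usable set 14, 21, 28) |
| Same plus day 30 | day 30 | 1–14 (21, 28, 30 spans only 9 days) |
| Daily | day 30 | 1–16 |
| Days 7, 14, 21, 28, 35, 42 | day 42 | 1–28 (last usable set 28, 35, 42) |

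Adding counts without moving the confirmation date leaves the late onsets open. Moving the date without adding counts leaves no required data. Both changes are needed.

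**Step 4: repeat doses.** A second dose on day 28 comes 2 days before the first dose's day-30 reading, and the schedule then restarts. In that case the new day-7 and day-14 visits fall on days 35 and 42 from the first dose (28 + 7 and 28 + 14). A later repeat dose breaks this alignment, so the plan has to say which infusion counts.

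**The case against.** The strongest reply is that the endpoint is clinically triggered. A patient with a low ANC who is failing growth factor is having counts followed. Section 4.1 restricts enrollment to patients cared for in the integrated transplant program, section 4.2.2 says routine post-transplant care continues, and section 4.2.1 allows additional assessments. Table 4.2.2 is also not a full list of study data: overall survival has no row. Section 6.2 collects adverse events for 28 days and serious adverse events for one year after the last dose. Nor does section 3.1.9 say that classification closes at day 30.

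Much of this stands. A reader might infer that the endpoint cannot be determined at all, and the documents do not support that: chart review of routine counts or serious event reports could recover cases. What the reply does not supply is a named source. Liver function tests, steroid dose and viral loads are also treated as standard of care, yet the protocol lists them at named post-infusion visits (liver tests at days 7 to 42 and day 90). Blood counts are not listed in that way, and an adverse event report does not supply serial ANC values.

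Two further readings go too far:
- A reader might turn 14 of 30 days into 47% of cases missed. That assumes onset spread evenly over 30 days, and the documents give no onset distribution.
- A reader might take the single graft failure among 50 patients in the earlier third-party study (section 1.11.2) as the expected signal. That case was concomitant with leukemic relapse, which the present definition may exclude.

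**Conclusion.** The concern holds for the plan as written. Required assessments give 0 of at least 3 ANC values, so the definition cannot be met from them alone. Even with daily counts, onset after about day 16 cannot be confirmed at day 30 (day 17 if days are counted inclusively). The missing counts carry most of the weight, because the day-30 reading by itself loses only late onsets.

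The likely result is under-counting or uneven classification. How many cases that means cannot be estimated from the documents, since it depends on the onset distribution and on how often counts are drawn in routine care. The consequence is limited: the endpoint is secondary and descriptive, and no sample size, power or stopping boundary depends on it. It is worth correcting because it is a listed safety endpoint and the correction is cheap.

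**What to change.** 1. In section 3.1.9, and to match in the synopsis, define the endpoint as onset within 28 days of a stated VST infusion, with the 14-day persistence confirmed through the existing day-42 visit (28 + 14 = 42).
2. State which infusion starts the clock, and how onset and confirmation are handled when a repeat dose given from day 28 resets follow-up.
3. In Table 4.2.2 and the post-infusion list of section 4.2.2, add a blood count with differential at days 7, 14, 21, 28, 35 and 42, recorded from routine-care counts where these exist.

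The cost is a few sentences, one amended table row and one list item, modest extra data entry, and a draw at any of these visits where no routine count was taken. The statistical design does not change.

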4 PATIENT ENROLLMENT AND EVALUATION

4.1 Enrollment

The informed consent process will begin at recognition of subject eligibility and consent will be obtained per institutional practices before study therapy is initiated. This protocol will be discussed with eligible patients and, when appropriate, their guardians. Only patients who receive their care in the integrated Cell and Gene Therapy Transplant program at Texas Children's Hospital and Methodist Hospital are eligible for this study. Consent process will consist of two parts: a) screening consent and b) treatment consent

1. The screening portion consists of registering demographic data and patient eligibility data. The search for a suitable matched virus VST line is initiated if the patient is eligible. If a VST line is not available, the following data will be collected: demographic data, HLA type, infection type and follow up data.
2. If a suitable matched VST line is available, the principal investigator or designee discusses the available line with the treating physician. After enrollment in the treatment portion of the protocol patient can then receive the identified VST line if eligibility criteria are still met.
3. Patients will be assessed for eligibility for subsequent infusions by completing the eligibility form. If the patient is deemed eligible, the search for a subsequent VST line will be initiated.

All cell culture manipulations will be carried out in the Center for Cell and Gene Therapy GMP facility using current standard operating procedures (SOPs). After Quality Assurance testing is complete a Certificate of Analysis will be issued.

4.2 Study Monitoring

4.2.1 Follow-up Schedule

The Follow-up Schedule for scheduled study visits is outlined in Table 4.2.2

Follow-up Assessments: The timing of follow-up visits is based on the date of VST infusion. If a patient has multiple VST doses the schedule resets again at the beginning so follow up relates to the last VST dose. Additional follow up assessments may be done based on clinical and laboratory responses.

**Table 4.2.1
FOLLOW-UP SCHEDULE**

Assessment Time	(Days Post-Infusion)
1 week	7 days
2 weeks	14 days
3 weeks	21 days
4 weeks	28 days
5 weeks	35 days
6 weeks	42 days
3 months	90 days
6 months	180 days
12 months	365 days

4.2.2 Assessments

All assessments are considered standard-of-care unless identified below by “*.”

Pre-Infusion

1. History and physical exam including height and weight
2. Viral loads for EBV, adenovirus, CMV, HHV6, JC virus and BK virus
3. Complete acute GVHD staging and grading information including assessments of rash, diarrhea, nausea/vomiting, weight and liver function tests
4. CBC with differential, platelet count
5. Basic chemistry
6. Liver function tests (bilirubin, alkaline phosphatase, AST, ALT)
7. Tacrolimus/cyclosporine level if on these agents
8. Pregnancy test* if female patient of childbearing potential and has received a reduced intensity transplant regimen
9. Samples for research laboratory studies*

Post-Infusion

1. Viral load for the treated virus or viruses will be collected weekly at 1, 2, 3, 4 and 6 weeks, and 3 months post-infusion. Thereafter, viral load results will be followed until 12 months post infusion as clinically indicated. Additional time points may be analyzed as clinically indicated. If the treatment team is also measuring viral loads for other viruses we will follow these results.
2. Complete acute GVHD staging and grading information including assessments of rash, diarrhea, nausea/vomiting, weight and liver function tests weekly until Day 42

CHARMS Protocol v1.0 (10.30.13)	Version 5.0 (10.6.15)
Version 2.0 (12.09.13)	Version 6.0 (08.29.16)
Version 2.1 (03.07.14)	Version 7.0 (04.26.17)
Version 3.0 (06.17.14)	Version 8.0 (05.24.17)
Version 4.0 (11.06.14)	Version 9.0 (08.10.17)

3. Chronic GVHD evaluation (if present) at 3, 6, and 12 months
4. Liver function tests (bilirubin, alkaline phosphatase, AST, ALT) at 1, 2, 3, 4, 5 and 6 and 3 months.
5. Infusion-related toxicities within 24 hours and toxicity evaluation weekly until Day 30, and acute GVHD until Day 42.
6. Steroid dose weekly until Day 42, and at 3 and 6 months
7. Samples for laboratory studies at 1, 2, 3, 4, and, 6 weeks and 3 months: 30-40mls or 6-8 teaspoons will be collected at each time point. For recipients who weigh less than 10kg the amount will be reduced to 3mls/kg. Depending on clinical and laboratory viral responses samples may be collected at additional time points.*

Research laboratory studies will include:

Assessment of virus-specific immunity as measured by serum profiling, ELIspot, intracellular cytokine staining, multimer assays and/or other assays as they become available.

After the initial follow up for safety is complete at 30 days for toxicity and 42 days for GVHD, patients will continue to be followed per routine clinical care post transplant. We will perform laboratory follow-up studies for 3 months post-infusion or longer depending on clinical and laboratory viral responses and will assess these patients clinically at 3, 6 and 12 months to evaluate for any long term effects attributable to the VST infusion.

Table 4.2.2 REQUIRED ASSESSMENTS

	Baseline (Day 0)	7	14	21	28	35	42	90	180	365
History and physical exam	X									
CMV, EBV, adenovirus, HHV6 and/or BK virus load (if previously positive)	X	X	X	X	X		X	X		
Acute GVHD evaluation	X	X	X	X	X	X	X			
Chronic GVHD evaluation								X	X	X
Liver function tests (alkaline phosphatase, bilirubin, AST, ALT)	X	X	X	X	X	X	X	X		
Tacrolimus/cyclosporine levels*	X									
Pregnancy test ¹	X									
Infusion related toxicity evaluation	X ²	X	X	X	X ³					
Steroid dose	X	X	X	X	X	X	X	X	X	
Blood and serum for ancillary laboratory studies	X ⁴	X ⁴	X ⁴	X ⁴	X ⁴		X ⁴	X ⁴		
Infections	X	X	X	X	X		X	X		
CBC with Differential	X									
Basic Chemistry	X									

* If on these agents

¹ Pregnancy test if of child bearing potential and has received a reduced intensity transplant

² This evaluation should be done within 24 hours of infusion

³ This evaluation should be done on day 30.

⁴ Research procedures beyond that required for usual care - 30-40mls or 6-8 teaspoons will be collected at each time point. For recipients who weigh less than 10kg the amount will be reduced to 3mls/kg. Depending on clinical and laboratory responses samples may be collected at additional time points before or after 90 days.

CHARMS Protocol v1.0 (10.30.13)	Version 5.0 (10.6.15)
Version 2.0 (12.09.13)	Version 6.0 (08.29.16)
Version 2.1 (03.07.14)	Version 7.0 (04.26.17)
Version 3.0 (06.17.14)	Version 8.0 (05.24.17)
Version 4.0 (11.06.14)	Version 9.0 (08.10.17)

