2.4.2 Administration and Monitoring

2.4.2.1 Partially HLA-matched VSTs will be thawed and given by intravenous injection. Patients will receive 2×10^7 partially HLA-matched VSTs/m² as a single infusion. In the rare case where insufficient banked cell product is available, a lower number of cells may be infused after discussion with the principal investigator, patient and/or guardian and the treatment team.

2.4.2.2 Premedications: Patients without prior history of reaction to blood products generally do not require premedication. If patients receive premedication, Benadryl 0.25-0.5mg/kg (max 25 mg) IV/po and/or Tylenol 5-10 mg/kg (max 650 mg) po/iv may be given.

CHARMS Protocol v1.0 (10.30.13)	Version 5.0 (10.6.15)
Version 2.0 (12.09.13)	Version 6.0 (08.29.16)
Version 2.1 (03.07.14)	Version 7.0 (04.26.17)
Version 3.0 (06.17.14)	Version 8.0 (05.24.17)
Version 4.0 (11.06.14)	Version 9.0 (08.10.17)

2.4.2.3 Patients will be monitored according to institutional standards for administration of blood products and at a minimum will be monitored according to below:

- Patients should remain in the clinic for at least one hour
- Patients should remain on continuous pulse oximetry for at least 30 minutes
- Vital signs should be monitored at the end of infusion then at 30 and 60 minutes

2.4.2.4. Supportive Care: Patients will receive supportive care for acute or chronic toxicity, including blood components or antibiotics, and other intervention as appropriate.

2.4.2.5 If a patient 1) receives medication (such as steroids), which may affect the persistence or function of the infused VST, or 2) does not have a complete response to their initial infusion, did not experience a significant toxicity to their initial infusion, and if alternative treatment options are not available or associated with unacceptably high risk of side effects (e.g. count suppression or renal disease), they are eligible to receive up to 4 additional doses at the same initial dose at day 28 post-infusion and at a minimum 2 week interval thereafter. If the additional doses are post steroid administration, the steroid dose must be decreased to a dose of 0.5 mg/kg/day of Prednisone (or equivalent) or lower before the patient may receive additional doses.

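### Research blood is limited per kg only below 10 kg and only per draw, with no cumulative limit across the schedule resets that follow each further dose

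*Combined protocol and SAP*

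**What the plan says.** Section 4.2.2 lists a baseline item, "Samples for research laboratory studies", and then post-infusion item 7, "Samples for laboratory studies at 1, 2, 3, 4, and, 6 weeks and 3 months". The volume is fixed: "30-40mls or 6-8 teaspoons will be collected at each time point". The only adjustment for body size is "For recipients who weigh less than 10kg the amount will be reduced to 3mls/kg".

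Footnote 4 of Table 4.2.2 repeats both rules, applies them to the baseline draw as well, and labels the draws "Research procedures beyond that required for usual care". Both places also allow samples at additional time points, without stating a number.

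Two other provisions decide how many draws a patient can have. Section 4.2.1 says: "If a patient has multiple VST doses the schedule resets again at the beginning so follow up relates to the last VST dose". Section 2.4.2.5 makes certain patients "eligible to receive up to 4 additional doses at the same initial dose at day 28 post-infusion and at a minimum 2 week interval".

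No weekly, monthly or whole-study limit on research blood appears at any weight in the available text.

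**The concern.** The protocol accepts that body weight should limit research blood and chooses 3 mL/kg, but the rule has two gaps. It stops at 10 kg, where the flat volume takes over and the per-kg amount can rise. It also applies to each draw separately, so it does not bound the total once the schedule restarts with further doses.

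The blood is taken for research, from transplant recipients. Small children are clearly expected: the under-10 kg rule exists, and section 4.1 names a children's hospital as one of the two sites. Section 2.3.1 item 5 admits patients with haemoglobin just above 8.0. The toxicity boundary in section 5.3 counts acute GVHD and non-hematologic events, so a fall in haemoglobin would not count towards it. What is at stake is an unbounded research burden on the smallest participants, not the trial's error rates.

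**Working it through.** The plan states no cumulative volume to reproduce. The one conversion it gives is consistent: 30/6 = 40/8 = 5 mL per teaspoon.

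**Inputs**
- Draw days after an infusion: 0, 7, 14, 21, 28, 42 and 90 (Table 4.2.2).
- Volume per draw: 30-40 mL from 10 kg up; 3 mL/kg below 10 kg (section 4.2.2).
- Doses: up to five in all, the first repeat at day 28 and the rest at least 14 days apart (section 2.4.2.5), so the earliest dates are days 0, 28, 42, 56 and 70.
- Reset: each new dose ends the running series and starts a new one (section 4.2.1). Draws falling on the same day are counted once.

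**Per-draw rule**
- At 10 kg: 30/10 = 3 mL/kg to 40/10 = 4 mL/kg.
- At 12 kg: 30/12 = 2.5 mL/kg to 40/12 = 3.33 mL/kg.
- The upper volume falls to 3 mL/kg at 40/3 = 13.3 kg.

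So between 10 and 13.3 kg a draw can exceed the 3 mL/kg set for smaller children.

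**Cumulative volume at 10 kg**: number of draws × 30-40 mL ÷ 10 kg

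| Doses on days | Draw days counted | Draws | Volume (mL) | mL/kg |
|---|---|---|---|---|
| 0 | 0, 7, 14, 21, 28, 42, 90 | 7 | 210-280 | 21-28 |
| 0, 28 | weekly, 0 to 56 | 9 | 270-360 | 27-36 |
| 0, 28, 42, 56, 70 | weekly, 0 to 98 | 15 | 450-600 | 45-60 |
| same five, last series completed | as above, plus 112 and 160 | 17 | 510-680 | 51-68 |

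**Other weights, 15 draws by day 98**
- Under 10 kg: 15 × 3 = 45 mL/kg.
- 12 kg: 450/12 to 600/12 = 37.5-50 mL/kg.
- 20 kg: 450/20 to 600/20 = 22.5-30 mL/kg.

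**Sensitivity of the five-dose figure at 10 kg, by day 98**
- Without the first day 0 draw: 14 draws, 42-56 mL/kg.
- If the series overlapped instead of resetting: 16 draws, 48-64 mL/kg.

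**Which gap matters more.** Applying 3 mL/kg at 10 kg lowers the five-dose upper figure from 60 to 45 mL/kg and leaves the lower figure unchanged. The missing cumulative limit is the larger gap.

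**The case against.** The five-dose figure is a corner case. It needs all five doses, each at the shortest interval, in a child of 10 kg, and the full 40 mL each time for the upper value. Further doses depend on response, toxicity, the lack of alternatives, an available line and the agreement of the patient, treating physician and investigator (sections 2.4.2.5 and 2.4.1.4). The documents do not say how many recipients will weigh 10 to 13.3 kg or how many will be re-dosed. This stands, which is why the one-dose and two-dose figures are given alongside.

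The step at 10 kg is also mild: 30 mL at 10 kg is exactly 3 mL/kg, so the anomaly arises only when staff draw more than that within the permitted range. That stands too.

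A limit might exist in the consent pages, which were not available, and the documents give no blood-volume standard. Whether any of these totals is excessive therefore cannot be judged from them.

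Three stronger readings are tempting and are not supported.
- A reader might infer from Table 4.2.2 that a blood count is required only once. The reset that multiplies the draws also brings back the baseline column, so a count recurs at each dose.
- A reader might infer that sampling lowers haemoglobin enough to decide which patients are re-dosed, since the haemoglobin criterion also applies to later infusions. Section 2.4.2.4 provides for blood components, and nothing in the documents quantifies any fall.
- A reader might infer that the weekly research draws could simply be left out after a further dose. The synopsis lists immune reconstitution at 1, 2, 3, 4 and 6 weeks and VST persistence as secondary endpoints, and section 2.4.2.5 allows later doses from a different donor. Those early samples would track a new line. The exploratory label in section 5.4 is attached to the modelling, not to the descriptive summaries and paired tests.

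**Conclusion.** The point holds as a gap in the sampling rule. The 3 mL/kg protection ends at 10 kg, leaving a band up to 13.3 kg where a draw can reach 4 mL/kg, and at no weight does the available text bound the total across resets. A 10 kg child already gives 21-28 mL/kg with a single dose, so the gap does not depend on the extreme schedule; 45-60 mL/kg is the upper end of what five doses permit by day 98.

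These totals assume that every scheduled research draw is taken, that the baseline draw is included and that same-day draws are shared. They exclude optional extra samples and blood drawn for clinical care. Section 2.4.2.5 also says that the re-dosing process may be repeated as needed; the count stops at five doses.

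No primary endpoint, error rate or planned analysis is shown to be affected. This is a low-cost improvement in participant protection, and it rests on the protocol's own per-kg figure rather than on any outside threshold.

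**What to change.** In section 4.2.2 item 7 and footnote 4 of Table 4.2.2:

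1. State the research draw volume for every recipient as the lesser of 30-40 mL and 3 mL/kg.
2. Add a cumulative per-kg limit on research blood that carries across schedule resets and includes the optional extra samples. The sponsor and ethics board should set its value. If the consent documents already contain a limit, bring it into these two places.
3. State that when the limit is reached, research draws are reduced or skipped, while safety and viral-load assessments continue unchanged.

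This is a wording change. The cost is smaller research samples between 10 and 13.3 kg (at most 36 rather than 40 mL at 12 kg, for example) and some missed research time points in small re-dosed children. Those gaps would fall on the reconstitution and persistence endpoints. The weekly draws after a further dose otherwise stay in the schedule.
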